### **5.3.4 Week 4, Session 2**

18-24 hours prior to the scheduled light session, the patient will be instructed to apply study drug to all accessible lesions. At that visit the following will be performed:

The patients will complete an VASitch form and the data transcribed into the eCRF.

**Prior** to the light session, 5 mL of blood obtained and processed for serum hypericin levels.

**Prior** to the light session, a 12-lead ECG obtained including QT interval measurements.

Adequate application of the drug will be verified by a pink staining on visual inspection of lesions.

Each patient will bring in their jar of study drug to the clinic. The jar will be weighed by clinic staff in order to estimate the amount of drug applied.

5-10 minutes **before** the light session, lesions will be graded using the Erythema Grading Score.

The patient will undergo the light treatment (may require repositioning to assure that all lesions are being treated).

5-10 minutes after completion of the light session, lesions will be graded using the Erythema Grading Score. If the score is <1, the next light dose should be increased. If the Erythema score is 1, the subsequent dose should be held at the same dose. If the score is >1, the next dose should be lowered by at least 1 J/cm^2.

2 hours after completion of the light session, 5 mL of blood obtained for serum hypericin levels.

2 hours after completion of the light session, 12-lead ECG obtained including QT interval measurements.

Patients will be asked about any AEs experienced since the last light session and these will be recorded in the eCRF. Information on all unresolved, previously reported AEs will be obtained.

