#### 1.4.1 Dosing Regimen

HyBryte ointment will be applied to all accessible CTCL lesions by the patients following training by the site staff. Care will be taken to minimize application to other skin areas, and cover the treated area with opaque bandaging/clothing. The lesions will then be exposed to visible light using the Daavlin Series 7 Phototherapy Device with visible light lamps (FDA 510K approval K212510) 18-24 hours later starting at 5 J/cm^2 and titrated up until the treated lesions exhibit a mild erythema following the light session. Drug application/light session will be done twice a week (at least 2 calendar days apart) for 8 weeks. The light treatment will be performed at least 2 calendar days apart each week. Light treatment is not permitted on consecutive days.

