### **5.3.3     Week 1, Session 1; Week 1, Session 2; Week 2 Session 1; Week 2, Session 2; Week 3, Session 1; Week 3, Session 2; Week 4, Session 1**

18-24 hours after drug application, the patient will return to clinic for their light session using the Daavlin 7 Series Phototherapy Device with visible light lamps. At that visit the following will be performed:

The patient will complete an VASitch form and the data transcribed into the eCRF.

Adequate application of the drug will be verified by a pink staining on visual inspection of lesions.

Each patient will bring in their jar of study drug to the clinic. The jar will be weighed by clinic staff in order to estimate the amount of drug applied.

5-10 minutes **before** the light session, lesions will be graded using the Erythema Grading Score.

During the first session, 5 J/cm^2 of light will be administered. Subsequent light sessions will deliver light doses based on the Erythema Grading Score after the previous light treatment. If the Erythema score was <1, the next light dose should be increased as deemed appropriate by the PI. If the Erythema score is 1, the subsequent dose should be held at the same dose. If the score is >1, the next dose should be lowered.

The patient will undergo the light treatment (may require repositioning to assure that all lesions are being treated).

5-10 minutes **after** completion of the light session, lesions will be graded using the Erythema Grading Score. If the score is <1, the light dose should be increased in the next light session. If the Erythema score is 1, the subsequent dose should be held at the same dose. If the score is >1, the next dose may be lowered by at least 1 J/cm^2.

Patients will be asked about any AEs experienced since the last light session and these will be recorded in the eCRF. Information on all unresolved, previously reported AEs will be obtained.

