### **5.3.5 Week 5, Session 1; Week 5, Session 2; Week 6, Session 1**

18-24 hours prior to the scheduled light session, the patient will be instructed to apply study drug to all accessible lesions. At that visit the following will be performed:

The patients will complete an VASitch form and the data transcribed into the eCRF.

Adequate application of the drug will be verified by a pink staining on visual inspection of lesions.

Each patient will bring in their jar of study drug to the clinic. The jar will be weighed by clinic staff in order to estimate the amount of drug applied.

5-10 minutes before the light session, lesions will be graded using the Erythema Grading Score.

The light duration for the session to deliver the target dose of light determined by the Erythema Score of the previous treatment response of light will be calculated.

Patients will undergo the light treatment (may require repositioning to assure that all lesions are being treated).

5-10 minutes after completion of the light session, lesions will be graded using the Erythema Grading Score. If the score is <1, the next light dose should be increased. If the Erythema score is 1, the subsequent dose should be held at the same dose. If the score is >1, the next dose should be lowered by at least 1 J/cm^2.

Patients will be asked about any AEs experienced since the last light session and these will be recorded in the eCRF. Information on all unresolved, previously reported AEs will be obtained.

### 5.3.6 Week 6, Session 2

18-24 hours prior to the scheduled light session, the patient will be instructed to apply study drug to all accessible lesions. At that visit the following will be performed:

The patients will complete an VASitch form and the data transcribed into the eCRF.

Prior to the light session, 5 mL of blood obtained and processed for serum hypericin levels.

Prior to the light session, a 12-lead ECG obtained including QT interval measurements.

Adequate application of the drug will be verified by a pink staining on visual inspection of lesions.

Each patient will bring in their jar of study drug to the clinic. The jar will be weighed by clinic staff in order to estimate the amount of drug applied.

5-10 minutes before the light session, lesions will be graded using the Erythema Grading Score.

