#### **6.1 Light Session**

The amount of visible light to be delivered will start at 5 J/cm^2 and be titrated up until either the patient experiences a mild (Erythema Grade 1) response to the light treatment 5-10 minutes post-treatment or a dose of 25 J/cm^2 is reached, whichever occurs first. The

duration of light treatment is dictated by the light treatment table listed below ([Table 4](#)). Depending on the distribution of the patient's lesions, more than one position for light treatments may be necessary.

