## 6.11 Erythema Scoring

Approximately 5-10 minutes before and after the completion of light therapy, treated lesions will be graded for erythema with the worst, best, and “average” scores recorded. The reaction will be graded using the definitions in [Table 11](#).

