**Table 11: Skin Phototoxicity Grading**

Toxicity Grade: Erythema and/or Edema	Severity
Grade 0	No apparent reaction
Grade I	Mild
Grade II	Moderate
Grade III	Severe with edema
Grade IV	Life-threatening with vesication

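### The light-dose rule gives Grade III and IV skin reactions the same action as Grade II, and no erythema grade requires treatment to be withheld

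*Protocol*

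**What the plan says.** Light starts at 5 J/cm² and, under Protocol 6.1, is "titrated up until either the patient experiences a mild (Erythema Grade 1) response to the light treatment 5-10 minutes post-treatment" or until 25 J/cm² is reached. Table 11 has five grades, 0 to IV; Grade III is severe with edema and Grade IV is "Life-threatening with vesication".

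The dose rule has three branches. A score below 1 means increase, a score of 1 means keep the same dose (the word held there means maintained, not withheld), and a score above 1 means lower:

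- Sections 5.3.4 to 5.3.7 (Week 4 Session 2 to Week 8 Session 1): "If the score is >1, the next dose should be lowered by at least 1" J/cm².
- Section 5.3.3 (Week 1 Session 1 to Week 4 Session 1): one sentence calls for a lower dose without an amount; the other says "If the score is >1, the next dose may be lowered by at least 1" J/cm².

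Section 5.3.3 also says: "Subsequent light sessions will deliver light doses based on the Erythema Grading Score after the previous light treatment". Every light visit has a second grading, for example in 5.3.5: "5-10 minutes before the light session, lesions will be graded using the Erythema Grading Score". No action is attached to it, and the light treatment follows. Section 6.11 says that "treated lesions will be graded for erythema with the worst, best, and" average scores recorded; it does not say which of the three drives the dose. SAP sections 3 and 4.4.10 repeat the titration and the grading and add no hold.

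**The concern.** Hypericin's dose-limiting toxicity when given systemically was phototoxicity (Protocol 1.1.2), so the response to a severe skin reaction is the central safety rule of the light schedule. As written, that rule does not separate a moderate reaction from severe edema or a life-threatening one, and it never calls for a pause.

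Timing adds to this. The post-session grade is taken 5 to 10 minutes after light. A reaction that develops later is first graded just before the next session, at a check that changes nothing that day. By then the ointment has normally been applied 18 to 24 hours earlier, so that check is the last scheduled chance to withhold light.

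At stake is a patient with severe edema who receives ointment and light again at the next session, at a slightly lower dose, with the site in full compliance with section 5.3.

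**Working it through.** The plan states no figure on this point. The check compares texts and adds simple counts.

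**1. Grades against actions after light**

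| Table 11 grade | 5.3.3 (7 sessions) | 5.3.4 to 5.3.7 (8 sessions) | Hold required? |
|---|---|---|---|
| 0 | increase | increase | no |
| I | same dose | same dose | no |
| II | lower, no amount; or may lower by at least 1 J/cm² | lower by at least 1 J/cm² | no |
| III | as Grade II | as Grade II | no |
| IV | as Grade II | as Grade II | no |

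**2. Gradings per patient.** Sixteen sessions × 2 = 32. Post-session gradings that feed the rule: 7 (5.3.3) + 1 (5.3.4) + 3 (5.3.5) + 1 (5.3.6) + 3 (5.3.7) = 15. The other 16 pre-session gradings + 1 final post-session grading (5.3.9) = 17 drive no dose action (17/32 = 53.1%). None of the 32 requires a hold. The 1 J/cm² minimum is firm for 8 of the 15; the other 7 fall under 5.3.3.

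**3. Smallest cut where the minimum is firm.** The cut as a share of dose is 1/dose, and Table 4 durations agree:

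- 10 J/cm²: 1/10 = 10.0%. 21:39 = 1299 s and 19:29 = 1169 s; 130/1299 = 10.0%.
- 25 J/cm²: 1/25 = 4.0%. 54:07 = 3247 s and 51:57 = 3117 s; 130/3247 = 4.0%.
- 5 J/cm²: 1/5 = 20.0%. The result, 4 J/cm², has no row in Table 4, which begins at 5.

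**4. Do the general provisions supply a hold?**

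- Section 5.4: the investigator may withdraw a patient. Discretionary, and not tied to a grade.
- Section 8.4: the action taken for the next dose is recorded. No action is prescribed.
- Section 9.2: serious and potentially serious events are notified within 24 hours. Notification, not a pause.
- Section 13.1.3: monitors check that serious and life-threatening events are reported.
- Section 14: a change to remove an immediate hazard may be made at once. This concerns changes to the protocol, not a patient's next session.

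Grade IV meets an SAE criterion by its label (9.1). A Grade III reaction reaches the Medical Monitor under 9.2 only if it is serious or needs significant medical intervention (8.1.3).

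**5. Time to act.** Under section 1.4.1, "Light treatment is not permitted on consecutive days", so a 24-hour notice is normally due before the next light session. Ointment comes sooner. If sessions are S hours apart, the next application falls S − 24 to S − 18 hours after light. Assuming S = 48, that is 24 to 30 hours. The protocol's spacing is in calendar days, so S can be below 48 and the interval shorter. A hold therefore has to cover application as well as light.

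**The case against.** The strongest case against is that the gap is narrow and a competent site would fill it. The rule sets a minimum cut, so a larger one is allowed. Section 5.4 lets the investigator withdraw a patient on two separate grounds of clinical judgement. Adverse events are asked about at every light visit and at the supervised final application (5.3.8). Treatment is up to 16 sessions (4.1), so fewer are foreseen, and SAP 7.1 tabulates events that stop study drug separately from those that end participation. Titration aims at Grade 1. In Table 2, erythema affected 7 of 161 HyBryte patients (4.3%), and no blister, burn or edema term reached the 3% listing threshold.

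Most of this stands, and it limits how far the point goes. A reader might infer that life-threatening reactions go unreported, or that the protocol compels re-treatment. The documents support neither: Grade IV is reportable by its label, and the investigator may always stop. A reader might also take 1 J/cm² as a firm minimum throughout, or a step from 25 to 24 J/cm² after a Grade IV reaction as expected conduct. Section 5.3.3 sets no firm amount, and the 25 J/cm² case is an extreme because upward titration stops at Grade 1.

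What the objection does not supply is a required pause. Table 2 gives no severity, so it cannot show that Grade III reactions are rare.

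A second objection bears on the remedy. These lesions are red by nature (1.1.1, Table 5), and Table 11 does not separate disease from reaction. A crude pre-session trigger could hold treatment because of disease redness and cost primary-endpoint data. That is right, and the fix allows for it.

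**Conclusion.** The point holds in a limited form. Grades II to IV share one branch whose only action is a lower next dose, and no erythema grade before or after light requires a hold. The main exposure is a Grade III reaction that is neither serious nor potentially serious: following 5.3 as written allows re-treatment at the next session, and the Medical Monitor may not hear of it. For Grade IV the gap is only the absence of a required pause.

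The size in patients cannot be estimated. The documents give no counts by this grading, and about 6 patients are planned. The percentages above describe minimum compliance, not likely practice, and the 24 to 30 hours rests on an assumed 48-hour spacing. Section 7.2 cannot be seen in the public copy; the conclusion assumes that it contains no hold rule. This is a cheap improvement to patient protection, not a threat to the validity of the analysis.

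**What to change.** Keep the dose-lowering sentence for every grade above I, and in 5.3.3 change may to should. Then add to 5.3.3 to 5.3.7, with the matching grading step in 5.3.9:

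*If the worst-lesion score is Grade III or higher after light, or if a pre-session grading shows a Grade III or higher treatment reaction (worse than that lesion's grade before the first light session, not disease redness), do not give light, and withhold drug application and light until the reaction has resolved to Grade I or to that lesion's pre-treatment grade. Resume only after the PI has consulted the Medical Monitor, and at a dose at least 1 J/cm² below the dose that preceded the reaction. Held sessions are not made up. If the reaction followed 5 J/cm², the PI and Medical Monitor set the lower dose and its duration, because Table 4 has no row below 5 J/cm².*

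Tell the Medical Monitor of every Grade III or IV reaction, including one after the final session. If a hold is found at a pre-session grading, still take that visit's pre-light hypericin sample and ECG.

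Cost: a protocol amendment with IRB approval (section 14). The worst score is already recorded at both gradings; the site would also need to note the lesion concerned and its starting grade, because 6.11 asks only for worst, best and average. The downside is an occasional missed session. Three of the 16 (Week 4, 6 and 8 Session 2) carry hypericin samples and ECGs. A hold carried over from an earlier session may lose those. A hold found at the visit loses only the 2-hour sample and ECG at Week 4 or 8, and nothing at Week 6, where all measurements are taken before light.

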### **5.3.5 Week 5, Session 1; Week 5, Session 2; Week 6, Session 1**

18-24 hours prior to the scheduled light session, the patient will be instructed to apply study drug to all accessible lesions. At that visit the following will be performed:

The patients will complete an VASitch form and the data transcribed into the eCRF.

Adequate application of the drug will be verified by a pink staining on visual inspection of lesions.

Each patient will bring in their jar of study drug to the clinic. The jar will be weighed by clinic staff in order to estimate the amount of drug applied.

5-10 minutes before the light session, lesions will be graded using the Erythema Grading Score.

The light duration for the session to deliver the target dose of light determined by the Erythema Score of the previous treatment response of light will be calculated.

Patients will undergo the light treatment (may require repositioning to assure that all lesions are being treated).

5-10 minutes after completion of the light session, lesions will be graded using the Erythema Grading Score. If the score is <1, the next light dose should be increased. If the Erythema score is 1, the subsequent dose should be held at the same dose. If the score is >1, the next dose should be lowered by at least 1 J/cm^2.

Patients will be asked about any AEs experienced since the last light session and these will be recorded in the eCRF. Information on all unresolved, previously reported AEs will be obtained.

### 5.3.6 Week 6, Session 2

18-24 hours prior to the scheduled light session, the patient will be instructed to apply study drug to all accessible lesions. At that visit the following will be performed:

The patients will complete an VASitch form and the data transcribed into the eCRF.

Prior to the light session, 5 mL of blood obtained and processed for serum hypericin levels.

Prior to the light session, a 12-lead ECG obtained including QT interval measurements.

Adequate application of the drug will be verified by a pink staining on visual inspection of lesions.

Each patient will bring in their jar of study drug to the clinic. The jar will be weighed by clinic staff in order to estimate the amount of drug applied.

5-10 minutes before the light session, lesions will be graded using the Erythema Grading Score.

The light duration for the session to deliver the target dose of light determined by the Erythema Score of the previous treatment response of light will be calculated.

Patients will undergo the light treatment (may require repositioning to assure that all lesions are being treated).

5-10 minutes after completion of the light session, lesions will be graded using the Erythema Grading Score. If the score is <1, the next light dose should be increased. If the Erythema score is 1, the subsequent dose should be held at the same dose. If the score is >1, the next dose should be lowered by at least 1 J/cm^2.

Patients will be asked about any AEs experienced since the last light session and these will be recorded in the eCRF. Information on all unresolved, previously reported AEs will be obtained.

### 5.3.7 Week 7, Session 1; Week 7, Session 2; Week 8, Session 1

18-24 hours prior to the scheduled light session, the patient will be instructed to apply study drug to all accessible lesions. At that visit the following will be performed:

The patients will complete an VASitch form and the data transcribed into the eCRF.

Adequate application of the drug will be verified by a pink staining on visual inspection of lesions.

Each patient will bring in their jar of study drug to the clinic. The jar will be weighed by clinic staff in order to estimate the amount of drug applied.

5-10 minutes **before** the light session, lesions will be graded using the Erythema Grading Score.

Patients will undergo the light treatment (may require repositioning to assure that all lesions are being treated).

5-10 minutes **after** completion of the light session, lesions will be graded using the Erythema Grading Score. If the score is <1, the next light dose should be increased. If the Erythema score is 1, the subsequent dose should be held at the same dose. If the score is >1, the next dose should be lowered by at least 1 J/cm^2.

Patients will be asked about any AEs experienced since the last light session and these will be recorded in the eCRF. Information on all unresolved, previously reported AEs will be obtained.

### **5.3.8 Week 8, Session 2 Drug Application Visit**

Patients will be asked to attend the clinic for the last drug application. At that visit, the following will be performed:

5 mL of blood obtained and processed for serum hypericin levels.

The drug will be applied by the patient under supervision of the site personnel.

The weight of the drug container will be weighed prior and after application of the drug.

Patients will be asked about any AEs experienced since the last light session and these will be recorded in the eCRF. Information on all unresolved, previously reported AEs will be obtained.

### **5.3.9 Week 8, Session 2 Light Session Visit**

18-24 hours after application of study drug, patients will return to the clinic for their final light session. At that visit, the following will be performed:

The patients will complete an VASitch and Skindex-29 ([Appendix III](#)) forms and the data transcribed into the eCRF.

Adequate application of the drug will be verified by a pink staining on visual inspection of lesions.

**Prior** to the light session, 5 mL of blood obtained and processed for serum hypericin levels.

**Prior** to the light session, a 12-lead ECG obtained including QT interval measurements.

**Prior** to the light session, vitals will be taken (heart rate, respiratory rate, and sitting blood pressure).

**Prior** to the light session, a hematology panel will be drawn.

**Prior** to the light session, a clinical chemistry panel will be drawn.

5-10 minutes **before** the light session, lesions will be graded using the Erythema Grading Score.

The light duration for the session to deliver the target dose of light determined by the Erythema Score of the previous treatment response of light will be calculated.

Patients will undergo the light treatment (may require repositioning to assure that all lesions are being treated).

5-10 minutes **after** completion of the light session, lesions will be graded using the Erythema Grading Score.

2 hours **after** completion of the light session, 5 mL of blood obtained and processed for serum hypericin levels.

2 hours **after** completion of the light session, a 12-lead ECG obtained including QT interval measurements.

Patients will be asked about any AEs experienced since the last light session and these will be recorded in the eCRF. Information on all unresolved, previously reported AEs will be obtained.

